8.5.1.4. Treatment of Outliers in Pharmacokinetic Analysis

If a value is considered to be anomalous due to being inconsistent with the expected PK profile, it may be appropriate to exclude the value from the PK analysis. However, the exclusion of any data must have strong justification and will be flagged in data listing and documented in the CSR.

Any quantifiable predose concentration value will be considered anomalous and set to missing for the PK analysis. This will be set to 0 by default in Phoenix WinNonlin.

8.5.2. Presentation of Pharmacokinetic Data

If the actual time of sample collection deviates from the nominal time by more than $\pm 10\%$, the serum concentration will be flagged.

For serum concentration data the following rules will apply:

- Values that are BLQ will be set to 0 for the calculation of summary statistics.
- Arithmetic mean or median values that are BLQ will be presented as 0.

For PK parameters the following rule will apply:

Geometric mean and coefficient of variation will not be calculated for t_{last} or t_{max} .

8.5.3. Pharmacokinetic Statistical Methodology

No inferential statistical analyses are planned.

CCI

CCI

8.7. Safety and Tolerability Assessments

8.7.1. Adverse Events

All AEs will be coded using the Medical Dictionary for Regulatory Activities (MedDRA) Version 24.0 (or higher if a new version is issued during the study; see the DMP for more details).

A treatment-emergent adverse event (TEAE) will be defined as an AE that starts during or after dosing, or starts prior to dosing and increases in severity after dosing.

A treatment-related TEAE will be defined as a TEAE with a relationship related to the study treatment, as determined by the investigator.

All AEs will be listed. In addition to the data recorded in the database, the listings will include derived onset time and duration. Onset time will be calculated from the time of dosing for TEAEs only.

The frequency of subjects with TEAEs and the number of TEAEs will be summarized for the following categories:

- TEAEs (overall, serious, leading to discontinuation, and leading to death) by treatment
- TEAEs by severity and treatment
- Treatment-related TEAEs (overall, serious, leading to discontinuation, and leading to death) by treatment
- Treatment-related TEAEs by severity and treatment

The frequency of subjects will be summarized separately for TEAEs and treatment-related TEAEs by the following:

- System organ class, preferred term, and treatment
- Preferred term and treatment

For the AE data the following rules will apply:

- For the derivation of treatment-emergent status (applicable to all AEs): If the start date/time of an AE is incomplete or missing, an AE will be assumed to not be a TEAE, unless the incomplete start date/time or the end date/time indicates an AE started after dosing.
- For the derivation of treatment-related status (applicable to TEAEs only): If the study treatment relationship for a TEAE is missing, a TEAE will be assumed to not be a treatment-related TEAE.
- For the derivation of onset time (applicable to TEAEs only): If the start date/time of a TEAE is missing, onset time will not be calculated. If the start date/time of a TEAE is incomplete, where possible, the minimum possible onset time will be calculated and presented in ‘ \geq DD:HH:MM’ format (eg, if the date/time of dosing is 01MAY2019/08:00 and recorded start date/time of a TEAE is 03MAY2019, then the minimum possible onset time will be calculated by assuming a TEAE started at the first hour and minute of 03MAY2019 [03MAY2019/00:00], thus will be presented as onset time \geq 01:16:00 in the listing). If the start date of a TEAE is the same as the date of dosing but the start time of a TEAE is missing, an onset time will be presented as ‘ \geq 00:00:01’. Any clock changes will be accounted for in the derivation.
- For the derivation of duration (applicable to all AEs): If the end date/time of an AE is missing, duration will not be calculated. If the start or end date/time of an AE is incomplete, where possible, the maximum possible duration will be calculated and presented in ‘ \leq DD:HH:MM’ format (eg, if the start of an AE date/time is 01MAY2019/08:00 and its recorded end date/time is 03MAY2019, then the maximum possible duration will be calculated by assuming an AE ended at the last hour and minute of 03MAY2019 [03MAY2019/23:59], thus will be presented as duration \leq 02:15:59 in the listing). Any clock changes will be accounted for in the derivation.
- For the calculation of TEAE summary statistics: If the severity of a TEAE is missing, that TEAE will be counted under the ‘missing’ category.
- For the calculation of TEAE summary statistics: If a subject experienced multiple TEAEs with the same preferred term for the same treatment, this will be counted as 1 TEAE for that treatment under the maximum severity recorded.

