8.1.2. Calculation of the Summary Statistics

For continuous data the following rules will be applied:

- Missing values will not be imputed, unless specifically stated otherwise.
- Unrounded data will be used in the calculation of summary statistics.

- If the number of subjects with valid observations (n) <3, summary statistics will not be calculated, with the exception of n, minimum, and maximum.
- In general, as early termination data are not associated with any scheduled timepoint, they will be excluded from all calculations of summary statistics and statistical analyses. Exceptions may be made where justified.

For categorical data the following rules will be applied:

- For ordered categorical data (eg, AE severity), all categories between the possible minimum and maximum categories will be included, even if n = 0 for a given category.
- For non-ordered categorical data (eg, race), only those categories for which there is at least 1 subject represented will be included; unless specifically stated otherwise.
- Missing values will not be imputed, unless specifically stated otherwise. A ‘missing’ category will be included for any parameter for which information is missing. This will ensure that the population size totals are consistent across different parameters.

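### SAP 8.7.1 does not settle whether an adverse event with an undeterminable start is treatment-emergent, and its literal default leans towards undercounting

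*SAP*

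**What the plan says.** SAP 8.7.1 defines a TEAE as an AE that begins at or after dosing, or one that begins earlier and worsens afterwards. Protocol Appendix 1 leaves this definition to the SAP, and TEAEs are a secondary endpoint.

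For an incomplete or missing start date/time, SAP 8.7.1 sets a default: the AE "will be assumed to not be a TEAE, unless the incomplete start date/time or the end date/time indicates an AE started after dosing".

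The section then derives onset: "Onset time will be calculated from the time of dosing for TEAEs only". Three onset rules matter here:

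- A TEAE with a missing start gets no onset time.
- A TEAE with a partial start gets a minimum onset. In the SAP's example this is "calculated by assuming a TEAE started at the first hour and minute of 03MAY2019".
- A special branch begins "If the start date of a TEAE is the same as the date of dosing but the start time of a TEAE is missing". Onset is then shown as ≥ 00:00:01 (days:hours:minutes).

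The section treats two other missing items differently from each other. On relatedness: "If the study treatment relationship for a TEAE is missing, a TEAE will be assumed to not be a treatment-related TEAE". On severity: "If the severity of a TEAE is missing, that TEAE will be counted under the" missing category.

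**The concern.** The default and the onset rules appear to assume different things about the same records. The onset rules apply to TEAEs only, yet two of them cover records that the default, taken at its word, never lets become TEAEs. The end-date part of the exception has a related problem: knowing when an event ended does not show that it began after dosing.

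The direction of the default matters too. Under Protocol 7.5.1, a pre-dose event unrelated to study procedures is recorded as medical history, whereas any event after dosing through the end-of-study visit is an AE. A record in the AE data with an unknown start is therefore more likely to be post-dose than pre-dose. The literal default presumes the opposite.

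At stake is whether the TEAE tables depend on how a programmer reads one verb, in groups so small that a single subject is visible.

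**Working it through.** **Inputs.** The rules in SAP 8.7.1; its example dosing time, 01MAY2019/08:00; the group size of 8 in SAP section 4; the medical-history rule in Protocol 7.5.1.

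**The SAP's own figures.**
- Minimum onset: 03MAY 00:00 − 01MAY 08:00 = 40 h = 01:16:00, as stated.
- Maximum duration: 03MAY 23:59 − 01MAY 08:00 = 63 h 59 min = 02:15:59, as stated.

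**The dosing-day branch.** The general method applied to an untimed event on 01MAY gives 00:00 − 08:00 = −8 h. The special branch shows ≥ 00:00:01 instead. It appears to be written for exactly this record, and it presumes a post-dose start.

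**The end-date exception.** An end at time E tells us only that the start was no later than E. If E is before dosing, the start was before dosing. If E is after dosing, the start can lie on either side. An end therefore never shows a post-dose start by itself.

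**Enumeration.** Take three undeterminable starts: fully missing; month only, in the dosing month; dosing date without a time. Cross them with five ends: missing; before dosing; same day after dosing; 2 days after; 40 days after. That gives 3 × 5 = 15 logical cases. They are not an expected data rate. All three starts behave alike:

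| End of the AE | Cases | Literal reading (start shown to be post-dose) | Looser: a post-dose end counts as an indication | Loosest: a post-dose start is not ruled out |
|---|---|---|---|---|
| Missing | 3 | not TEAE | not TEAE | TEAE |
| After dosing | 9 | not TEAE | TEAE | TEAE |
| Before dosing | 3 | not TEAE | not TEAE | not TEAE |
| **TEAEs of 15** | | **0** | **9** | **12** |

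On the literal reading the end-date exception, the missing-start onset rule and the untimed dosing-day onset rule are all empty. On either looser reading all three have cases. The worsening part of the TEAE definition does not rescue them, because the missing-date default makes no exception for it.

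A start on a known later day without a time (03MAY in the example) is a TEAE on every reading.

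**Size per subject.** If a subject's only event in a row is reclassified, that row moves by 1/8 = 12.5 percentage points. A single severity row can also rise, because repeats of a preferred term are handled so that "this will be counted as 1 TEAE for that treatment under the maximum severity recorded". For example, suppose a subject has the same term twice: moderate on the dosing day with no time, and mild on a known later day. The literal default moves that subject out of the moderate row (−12.5) and into the mild row (+12.5), with the overall row unchanged.

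**The case against.** The strongest reply is that a text should be read so that every clause has effect. The dosing-day branch shows what the authors expected, so *indicates* should be taken loosely, and then no clause is empty. That stands as far as it goes: a reader might infer that the SAP contradicts itself or is certain to lose dosing-day events, and the documents support neither. But the SAP does not state the looser reading, and the two looser readings differ from each other on an untimed dosing-day event with no recorded end. The rule still needs one stated meaning.

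A second reply is that few records will be affected. Subjects are resident on Day 1 and questioned at least daily, source data are verified, queries are resolved, and the SAP's onset format presupposes clock times. The AEs that led to Amendment 2 occurred after Day 4, so with a recorded date they are untouched. All AEs are listed whatever their flag. Escalation to Group 2 rests on a full review of available safety data, and no inferential analysis is planned. All this limits the size. It does not remove the ambiguity, and Protocol Appendix 1 names only the dates of onset and resolution, without saying whether a time is mandatory.

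A reader might also infer that the relatedness default breaks the SAP's own missing-data rule. It does not. SAP 8.1.2 says "Missing values will not be imputed, unless specifically stated otherwise", and 8.7.1 states such an exception. Protocol Appendix 1 also obliges the investigator to assess causality for every event, so missing relatedness should be rare. Treating relatedness and severity differently is uneven, not an error.

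**Conclusion.** The point holds as an ambiguity in the TEAE derivation, joined to a default that leans the wrong way if applied literally. Three clauses are empty on the literal reading and live on a looser one. The literal default can lower the overall TEAE counts or leave them unchanged, never raise them.

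The practical effect is probably small and may be zero. The documents give no rate of missing start dates or times, and none is assumed here. The 12.5 points assume the planned 8 subjects per group and one affected subject with no other event in that row. That an undated AE is more likely post-dose is an inference from what Protocol 7.5.1 sends to medical history, not a figure in the documents. It is worth correcting because the remedy is cheap and the rule defines a secondary endpoint.

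**What to change.** In SAP 8.7.1, before database lock:

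1. Treat an AE with a missing or partial start as a TEAE unless the available start or end date/time, or other recorded information, shows that it started before dosing. The worsening part of the TEAE definition continues to apply to events shown to start before dosing. Because Protocol Appendix 1 keeps one record at worst severity, later worsening has to come from recorded information or a resolved query.
2. State that a dosing-day AE with no clock time is a TEAE unless the record shows that it began before dosing, for example through an end time before dosing or an entry tying it to a pre-dose procedure. This agrees with the existing ≥ 00:00:01 branch.
3. Optionally, for consistency with severity, show missing relatedness in its own category.

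The cost is a few lines of text and derivation code. The downside is that an occasional pre-dose, procedure-related AE with a partial date may be counted as a TEAE. Protocol 7.5.1 does put such events in the AE data. A narrower change, which defines *indicates* and adds item 2 alone, would remove much of the ambiguity but would leave the default's direction in place for AEs with neither a start nor an end.

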8.7.2. Clinical Laboratory Parameters

All clinical laboratory parameters, their changes from baseline, will be listed, as applicable; any value outside the clinical reference range will be flagged. Separate listings will be provided for any parameter for which there is any individual subject value outside the respective clinical reference range.

Summary tables and boxplots by treatment and timepoint will be provided by treatment group for clinical chemistry and hematology parameters, their changes from baseline, as applicable.

Values recorded as $< x$, $\leq x$, $> x$, or $\geq x$ will be displayed in the listings as recorded. For the derivation of listing flags, all calculations, and presentation in the figures, $< x$ and $\leq x$ values will be set to 0, whereas $> x$ and $\geq x$ values will be set to x .

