3. INVESTIGATIONAL PLAN

3.1. Overall Study Design and Plan

This will be a Phase 1, single-center, open-label, sequential-group study to investigate the safety, tolerability, and PK of a single SC dose of AMG 592 in 2 groups of healthy Chinese subjects and 1 group of healthy Japanese subjects. In addition, a group of healthy Caucasian subjects will be evaluated at the high dose level for comparison.

Approximately 32 subjects will be enrolled in total, with ^{cc} subjects in each of the following 4 groups:

- Group 1: Chinese subjects (n=■) will receive ^{CCI} ■ AMG 592 given as one ^{CCI} ■ SC injection
- Group 2: Chinese subjects (n=■) will receive ^{CCI} ■ AMG 592 given as one ^{CCI} ■ SC injection
- Group 3: Japanese subjects (n=■) will receive ^{CCI} ■ AMG 592 given as one ^{CCI} ■ SC injection
- Group 4: Caucasian subjects (n=■) will receive ^{CCI} ■ AMG 592 given as one ^{CCI} ■ SC injection.

Potential subjects will be screened to assess their eligibility to enter the study within 28 days prior to dose administration.

Under the initial study design and plan prior to Amendment 2 of the protocol, ^{CCI} ■ ^{cc} subjects in Group 1 and all subjects in Groups 3 and 4 had been enrolled, dosed, and had remained in the CRU up through the earliest discharge day on Day 3. Due to the occurrence of adverse events in subjects administered with AMG 592 reported thus far in the study after day 4 and during the period after discharge from the CRU, enrollment of the remaining ^{cc} subjects in Group 1 was placed on temporary hold. The intention of the hold was to allow a full evaluation of emerging safety data and to prepare protocol amendment 2.

Under Protocol Amendment 2, the overall study design and plan will be conducted as follows, for the remaining ^{cc} subjects in Group 1 (Chinese cohort, ^{CCI} ■) and all subjects in Group 2 (Chinese cohort, ^{CCI} ■):

Eligible subjects will be admitted into the CRU for Check-in on Day -1 and be confined to the CRU until clinic discharge on Day 7. Individual subjects may be required to remain in the CRU for safety observations beyond Day 7 (to a maximum of Day 11) at the discretion of the Investigator, based on the emergence and progression of adverse events and other signs and symptoms requiring monitoring. Each subject will participate in 1 treatment group only.

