- The Investigator is obligated to perform or arrange for the conduct of supplemental measurements and/or evaluations as medically indicated or as requested by the Sponsor to elucidate the nature and/or causality of the adverse event or serious adverse event as fully as possible. This may include additional laboratory tests or investigations, histopathological examinations, or consultation with other health care professionals.
- If a subject is permanently withdrawn from protocol-required therapies because of a serious adverse event, this information must be submitted to the Sponsor.
 - If a subject dies during participation in the study, the Investigator will provide the Sponsor with a copy of any post-mortem findings including histopathology.
- New or updated information will be recorded in the originally completed eCRF.
- The Investigator will submit any updated serious adverse event data to the Sponsor within 24 hours of receipt of the information.

Reporting of Serious Adverse Event

Serious Adverse Event Reporting via Paper Serious Adverse Event Report Form

- Facsimile transmission of the Serious Adverse Event Report Form (see [Figure 2](#)) is the preferred method to transmit this information.
- In rare circumstances and in the absence of facsimile equipment, notification by telephone is acceptable with a copy of the Serious Adverse Event Report Form sent by overnight mail or courier service.
- Initial notification via telephone does not replace the need for the Investigator to complete and sign the Serious Adverse Event Report Form within the designated reporting time frames.

Figure 2: Sample Serious Adverse Event Report Form

AMGEN 20200102 LabCorp Study # 8448873 AMG 592	Clinical Trial Serious Adverse Event Report – Phase 1–4 Notify Amgen Within 24 Hours of knowledge of the event				 New  Follow-up	
Amgen (Sponsor) UK Safety Fax Number: [name] If FAX is unavailable, email form to the following address: [contact]						

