^b Inhouse residency from Day 1 through the completion of all assessments on Day 7. Solid line indicates time that subjects are required to stay in the CRU. Dashed line indicates that subjects may stay in the CRU after Day 7 until a maximum of Day 11 if they choose (to reduce travel and accommodation burden on subjects); alternatively, the Investigator may require subjects to remain in-house for 1 or more days after Day 7 (up to Day 11) at their discretion, based on other signs and symptoms requiring monitoring. Only subjects enrolled after Amendment 2 will have discharge study procedures completed on Day 7 at the earliest. (All other subjects enrolled prior to Amendment 2 had discharge study procedures completed by Day 3 at the earliest.) The latest discharge day for all subjects is Day 11.

^c Physical examination to include a neurological examination. A full PE will be conducted at Screening and at discharge (Day 7 at the earliest). A symptom-directed PE will be conducted on Days -1, 3, 11, 22, 29, and 43/EOS. Only subjects enrolled after Amendment 2 will have discharge study procedures completed on Day 7 at the earliest. (All other subjects enrolled prior to Amendment 2 had discharge study procedures completed by Day 3 at the earliest.) The latest discharge day for all subjects is Day 11.

^d Interim medical history only.

^e Electrocardiogram (ECG) will be single 12-lead ECG, prior to blood draws or invasive procedures.

^f Supine blood pressure (BP), supine heart rate, respiratory rate, and oral body temperature. Heart rate and BP will be measured using the same arm for each reading after the subject has been resting in the supine position for at least 5 minutes. For subjects enrolled after Amendment 2, additional days for vital signs measurements will include Days 4, 5, 7, 15, and 29.

^g Adverse events will be recorded from initiation of study treatment on Day 1 until the EOS. Any events prior to study drug administration but deemed by the Investigator to be related to study procedures will be reported as adverse events.

^h Serious adverse events will be recorded from the time the subject signs the informed consent form until the EOS.

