ⁱ Prior and concomitant medication administration will be recorded beginning at informed consent. Also, all Investigator-approved medications taken by a subject within 30 days or 5 half-lives (whichever is longer) before Day 1 for over-the-counter or prescription medications, and 30 days prior to Check-in for herbal medicines (eg, St. John's wort), vitamins, or supplements will be recorded on the subject's electronic case report form.

^j Performed in serum at Screening and in urine at all other times for all females. A positive urine pregnancy test will be confirmed with a serum pregnancy test.

^k Subjects will be fasted overnight (at least 8 hours) before collection of blood samples for clinical laboratory evaluations. Only subjects enrolled after Amendment 2 will have additional chemistry and hematology laboratory evaluations on Days 2, 5, and 7 and will have the additional urinalysis procedure at discharge (Day 7 at the earliest). (All other subjects enrolled prior to Amendment 2 had urinalysis conducted at discharge on Day 3 at the earliest.)

^l The eGFR will be calculated using the Modification of Diet in Renal Disease equation.

^m Performed in females only.

ⁿ Blood samples for determination of AMG 592 serum concentrations and PK parameters will be collected: Predose; 6, 12, and 16 hours postdose; and on Days 2 (24 hours postdose), 3, 4, 5, 6, 8, 11, 15, 22, 29, and 43 (EOS) following administration of AMG 592 on Day 1. The postdose samples collected on Days 1 and 2 (6, 12, 16, and 24 hour samples) will have a sampling window of \pm 30 minutes, postdose samples collected on Days 3 and 4 will have a sampling window of \pm 6 hours, postdose samples collected on Days 5 through Day 15 will have a sampling window of \pm 1 day, postdose samples taken on Days 22 and 29 will have a sampling window of \pm 2 days, and postdose samples taken on Day 43 (EOS) will have a sampling window of \pm 4 days. Times of all PK samples will be recorded to the nearest minute.

^o Only subjects enrolled after Amendment 2 will have additional biomarker development sample assessment on Day 3.

Approval Signatures

Document Name: Protocol Amendment efavaleukin alfa 20200102 2

Document Description: A Phase 1, Open-label, Sequential-group, Single-dose Study to Evaluate the Safety, Tolerability, and Pharmacokinetics of AMG 592 Administered Subcutaneously in Healthy Chinese, Japanese, and Caucasian Subjects

Document Number: CLIN-000265267

Approval Date: 29 Apr 2022

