The mutation in the IL-2RB-binding region of IL-2 results in increased dependence on CD25 for IL-2R signaling compared with wild-type IL-2. Thus, efavaleukin alfa preferentially drives this positive feedback loop in Treg over effects on other lymphocytes (ie, other T cells and ILC2 which may express CD25 but do not express FOXP3, and NK cells which express little or no CD25 and no FOXP3). Compared with aldesleukin, efavaleukin alfa exhibits greatly improved selectivity for Treg over Tcon and NK cells both in vitro and in vivo, potentially resulting in an improved therapeutic margin. In addition, the Fc domain of AMG 592 confers a prolonged half-life compared with aldesleukin, thus reducing the dosing frequency required to maintain Treg enrichment

Nonclinical in vitro and in vivo studies have demonstrated that AMG 592 exhibits greater selectivity for inducing Treg expansion over the expansion of CD4 and CD8 T cells, and NK cells, relative to low dose, recombinant IL-2. This greater selectivity of AMG 592 has promise for greater efficacy and a wider therapeutic margin in inflammatory diseases relative to low-dose recombinant IL-2-based modalities.

Amgen is developing AMG 592 as a treatment for multiple inflammatory diseases including systemic lupus erythematosus (SLE), steroid-refractory chronic graft-versus-host disease (GvHD), and ulcerative colitis. This study is designed to evaluate whether pharmacokinetic (PK) and safety data in Chinese and Japanese subjects are similar to those from the global population.

A summary of completed and ongoing clinical studies for AMG 592 is provided in the IB.¹

Changes to Study Protocol 20200102

The current study (20200102) was placed on a temporary hold during recruitment of the Japanese CCI cohort due to the occurrence of delayed-onset AEs in the majority of subjects administered AMG 592 thus far in the study. The intention of the hold was to prepare a protocol amendment which would allow for the PI to direct that subjects should remain in the CRU beyond Day 3 for longer observation for delayed-onset AEs. As of 27 Sept 2021, [] subjects in the Caucasian cohort and [] subjects in the Japanese cohort had been enrolled, dosed, and completed all scheduled study procedures. The remaining [] Japanese subjects and all Chinese subjects will be enrolled under the amended protocol (Protocol Amendment 1).

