8.1.3. Repeat and Unscheduled Readings

For vital signs and 12-lead ECG data only, any predose value recorded in addition to the original value or a postdose value recorded within 15 minutes of the original value will be defined as a repeat value; any postdose value recorded more than 15 minutes after the original value will be defined as an unscheduled value. For all other data types (eg, laboratory parameters), any value recorded in addition to the original value will be defined as an unscheduled value.

The original value will be replaced by the last associated repeat value in all calculations, with the exception of the 12-lead ECG outlier analysis (see [Section 8.7.4](#)).

As unscheduled values are not associated with any scheduled timepoint, they will be excluded from all calculations, with the exception of the baseline derivation (see [Section 8.1.4](#)) and 12-lead ECG outlier analysis (see [Section 8.7.4](#)).

8.1.4. Definitions of Baseline, Change from Baseline, Percent Change from Baseline and Fold Change from Baseline

The baseline will be defined as the value recorded prior to dosing. If the date/time of the value is incomplete or missing, it will be excluded from the baseline calculation, unless the incomplete date/time indicates the value was recorded prior to dosing.

Individual changes from baseline will be calculated by subtracting the individual subject’s baseline value from the value at the postdose timepoint.

Fold Change from baseline = (Final Value / Baseline Value);

The summary statistics for change from baseline and fold changes from baseline will be derived from individual subjects’ values (eg, mean change from baseline will be the mean of

the individual changes from baseline for all subjects, rather than difference between the mean value at the postdose timepoint and mean value at baseline).

See [Section 8.1.3](#) for more detail on handling repeat and unscheduled readings in the calculations.

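### Does the SAP need a rule for comparing laboratory safety between Group 2 and Groups 3 and 4, which were tested on different draw schedules?

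*SAP*

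**What the plan says.** SAP 8.7.2 plans that "Summary tables and boxplots by treatment and timepoint will be provided by treatment group for clinical chemistry and hematology parameters". It also lists all laboratory values, flags those out of range, and gives separate listings for any parameter with an out-of-range value. SAP 8.7.3 handles vital signs in the same by-timepoint way.

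The schedule differs by amendment. Protocol Appendix 8, footnote k: "Only subjects enrolled after Amendment 2 will have additional chemistry and hematology laboratory evaluations on Days 2, 5, and 7". Footnote f: "For subjects enrolled after Amendment 2, additional days for vital signs measurements will include Days 4, 5, 7, 15, and 29". Protocol 3.1 records that before Amendment 2 "all subjects in Groups 3 and 4 had been enrolled, dosed, and had remained in the CRU". Group 2 and the rest of Group 1 come under Amendment 2.

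The enrollment hold followed adverse events "reported thus far in the study after day 4 and during the period after discharge from the CRU". Section 1.1 of Amendment 1 describes "delayed-onset AEs in the majority of subjects administered AMG 592 thus far in the study".

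On extra tests, Protocol Appendix 1 makes the investigator "obligated to perform or arrange for the conduct of supplemental measurements and/or evaluations as medically indicated". For laboratory values outside the schedule, SAP 8.1.3 says: "As unscheduled values are not associated with any scheduled timepoint, they will be excluded from all calculations" (baseline and the ECG outlier analysis excepted).

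SAP Section 4 recounts the hold, which groups fall on which side of Amendment 2, and the different discharge and visit days. The general caution in SAP 8.1 concerns only sample size.

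**The concern.** Protocol 1.1 gives as an aim to see whether safety in Chinese and Japanese subjects resembles that of the global population. The comparison of Group 2 with Groups 3 and 4 is fully confounded with amendment version. A silent laboratory abnormality is found only if blood is drawn, and in the days that prompted the hold only Group 2 has scheduled draws. With identical true rates, Group 2 could show more abnormalities, and a reader could take that for an ethnic difference.

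Three features add to the worry. Tests ordered for Groups 3 and 4 in that window stay out of the summaries. Amendment 2 also changed some exclusions that bear on the liver. And the SAP foresees splitting data by COVID-19 impact (8.1.1) but says nothing about this known split.

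**Working it through.** **Inputs.** Draw days: Protocol Appendix 8 with footnote k. Sample counts: Appendix 3 of Amendments 1 and 2. Group size 8: SAP Section 4. Onset, duration, share affected and share judged clinically significant are assumptions, because the documents give none.

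**1. The documents' own counts.** Amendment 2: 9 laboratory samples × 7.5 mL = 67.5 mL, as stated. Amendment 1: 6 × 7.5 = 45 mL, as stated. Removing Screening and Check-in leaves 7 postdose draws (Days 2, 3, 5, 7, 11, 22, 43) against 4 (Days 3, 11, 22, 43). In Days 4 to 10 that is 2 against 0. The longest gap up to Day 11 is 11 − 7 = 4 days against 11 − 3 = 8.

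**2. What the planned tables compare.**

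| Day | Group 2 | Groups 3 and 4 |
|---|---|---|
| 2, 5, 7 | drawn | no scheduled draw |
| 3, 11, 22, 43 | drawn | drawn |

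Each row stands alone, so the two schedules are never averaged. On the four common days the schedule is the same. On the other three there is nothing to set against Group 2. SAP 6 adds an Overall column at one (redacted) dose. If it includes Groups 2, 3 and 4, its n would be 8 on the added days against 3 × 8 = 24 on the common days, and n is among the summary statistics (SAP 8.1.2).

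**3. How unequal detection could be (illustration).** Assume onset uniform from Day 4 to Day 11 and duration L days. The chance that a scheduled draw catches the abnormality is:
- Groups 3 and 4: min(L, 7)/7
- Group 2: [min(L, 1) + min(L, 2) + min(L, 4)]/7

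| L (days) | Group 2 | Groups 3 and 4 | Gap |
|---|---|---|---|
| 1 | 3/7 = 43% | 1/7 = 14% | 2/7 |
| 2 | 5/7 = 71% | 2/7 = 29% | 3/7 |
| 4 | 7/7 = 100% | 4/7 = 57% | 3/7 |
| 7 or more | 100% | 100% | 0 |

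With onset uniform over Days 2 to 11 instead, L = 2 gives 78% against 33%. The direction is robust; the size depends on the assumptions.

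**4. From detection to a TEAE count.** With L = 2 and half of 8 subjects affected, expected detections are 8 × 0.5 × 5/7 = 2.86 against 8 × 0.5 × 2/7 = 1.14, a difference of 1.71. With a quarter affected they are 1.43 against 0.57, a difference of 0.86. These are detections, which the SAP text does not tabulate as a rate. Protocol 7.5.2 says that abnormal results without clinical significance are in general not adverse events, and that where applicable the clinical sequelae are recorded instead. If 10% to 25% were judged significant (assumption), the excess in the TEAE tables is 1.71 × 0.10 = 0.17 to 1.71 × 0.25 = 0.43 subjects with half affected, and 0.09 to 0.21 with a quarter affected.

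**5. Symptom-based events.** Days on which subjects are questioned: Days 1 to 7 plus 8, 11, 15, 22, 29 and 43 = 13 under Amendment 2. Earlier: Days 1 to 6 plus the same six = 12. This is nearly equal.

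**6. Eligibility.** Exclusion 38, new in Amendment 2, requires raised ALT or AST together with raised bilirubin, at both Screening and Check-in; read literally, it removes few people. In exclusion 17 the named hepatitis tests were already in the serology panel of the earlier versions (Appendix 2); only the history clause is clearly new. Exclusion 10 (eGFR) moved from Screening or Check-in to Screening alone. Inclusion 4 bars clinically significant laboratory findings in every version. The net effect cannot be computed and is probably small.

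**The case for a change.** The strongest case for a change is that, with no inferential analysis planned, the side-by-side columns are the evidence. The TEAE tables pool all follow-up, so in groups of 8 one or two extra cases could change the reading. If each draw independently had a 5% chance of being out of range, the chance of at least one flag would be 1 − 0.95⁷ = 30.2% against 1 − 0.95⁴ = 18.5%, or 2.4 against 1.5 subjects of 8. The SAP was written with Amendment 2 in hand, and a caution, a flag and some footnotes would cost almost nothing.

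The facts in that case stand: the confounding is complete, the draws are unequal, and no analysis section links the two. The consequence does not follow. Subjects with any flagged value are not a planned summary in the SAP text. A caution or footnote would leave the TEAE tables, the one pooled summary exposed, exactly as they are. Basing laboratory statements on common days repeats what the by-timepoint layout already does. Tests ordered outside the schedule leave the calculations, not the listings: SAP 8.1 and 8.7.2 list and flag all values, so results from Days 4 to 10 in Groups 3 and 4 remain visible. AE listings carry onset time, so late events can be traced. Nor do the documents say that the events behind the holds were laboratory findings.

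Vital signs raise the same point with the same answer. Subtracting footnote f's added days gives 5 against 2 measurement days in Days 4 to 10. I could not confirm the earlier days from the schedule grids, whose columns do not line up in the copy I read.

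**Conclusion.** No change to the plan. The SAP leaves an interpretive sentence unwritten, but its Section 4 gives the reader the amendment history, and its by-timepoint tables and full listings keep the unequal days apart. An analyst writing the study report would note that Group 2 differs from Groups 3 and 4 in amendment version as well as ethnicity. Putting that in the SAP would alter none of the planned estimates or counts.

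The imbalance is real in the draws (7 against 4; 2 against 0 in Days 4 to 10). Its effect on TEAE counts cannot be computed from the documents; under the assumptions shown it is about 0.1 to 0.4 subjects of 8, and it vanishes for abnormalities lasting 7 days or more. This rests on assumed onset, duration and shares, and on the general rule in Protocol 7.5.2 being followed. The TFL shells were not available and the doses are redacted, so neither the footnotes nor the make-up of the Overall column could be checked.
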